### 8.1.11 Minimal Disease Activity

Minimal disease activity is a state of disease activity deemed a useful target of treatment by both the patient and physician, given current treatment possibilities and limitations. Criteria have been developed to determine whether a patient has reached MDA based on key outcome measures in PsA.

MDA will be assessed using component assessments from the same analysis visit, ie, after applying any visit mapping as outlined in [Section 3.5](#). MDA will only be assessed for visits at which all assessments (with the exception of BSA and PASI, see below) were planned to be collected.

A subject will be considered as having MDA if 5 or more of the following 7 criteria are fulfilled:

- TJC $\leq$ 1
- SJC $\leq$ 1

- $PASI \leq 1$  or  $BSA \leq 3$
- $PtAAP \leq 15$ mm
- $PGADA \leq 20$ mm
- $HAQ-DI \leq 0.5$
- Tender enthesial joints  $\leq 1$

The following additional rules will be applied:

- PASI or BSA
  - The criteria “ $PASI \leq 1$  or  $BSA \leq 3$ ” will be considered to be met if either of the 2 subcriteria are satisfied, even if the other assessment is missing. Note that a separate rule (as defined below) is applied for subjects with BSA affected by psoriasis of  $<3\%$  at PA0008 Baseline.
  - The criteria “ $PASI \leq 1$  or  $BSA \leq 3$ ” will be considered as a missing component (for OC) if only 1 subcriterion is available and this does not meet the condition for MDA
  - A subject with BSA affected by psoriasis of  $<3\%$  at PA0008 Baseline will always be considered to have met the criteria “ $PASI \leq 1$  or  $BSA \leq 3$ ”. This is the case because PASI and BSA are not planned to be measured at post-Baseline visits for subjects with BSA  $<3$  at PA0008 Baseline. However, if for some reason, PASI or BSA are measured post-PA0008 Baseline for such subjects, and the results indicate a  $PASI > 1$  or  $BSA > 3$ , then this criterion will be considered as not having been met.
- The MASES items will be used to assess whether a subject has  $\leq 1$  tender enthesial joint: if the total derived MASES score is  $\leq 1$  then the criterion will be considered met.
- If any component is missing then the criteria for that component will be considered to have not been met.
- In the case of partial data at a specific visit, if there are sufficient data to derive MDA as having been met eg, if results are available for 5 out of the 7 assessments and these fulfill the criteria above, this subject will be counted as having achieved MDA in the summary of observed case results. Similarly, if there are sufficient data to calculate non-response regardless of missing data, this subject will be included in the summary of OC results as not having MDA at the specific visit

Further details regarding these calculation algorithms and rules for handling missing components are provided in [Section 12.2](#)).

### 8.1.12 Disease Activity Score-28 based on C-reactive Protein

The components for DAS28(CRP) include the TJC and SJC based on 28 joints (see [Section 8.1.2](#)), CRP (mg/L), and the PGADA (mm). Any CRP values less than 0.16mg/L will be substituted as described in [Section 8.1.7](#) prior to calculating the DAS28(CRP) score.

If more than 50% of the planned joint assessments (ie, more than 14 assessments) are missing at a visit, then the TJC or SJC will be set to missing for that visit for the purposes of DAS28(CRP) calculation.

DAS28(CRP) is calculated as follows (where ‘ln’ represents the natural logarithm function):

$$DAS28(CRP) = 0.56 * \sqrt{TJC} + 0.28 * \sqrt{SJC} + 0.014 * PGADA + 0.36 * \ln(CRP + 1) + 0.96 \quad (15)$$

DAS28 (CRP) will be assessed using component assessments from the same analysis visit, ie, after applying any visit mapping as outlined in [Section 3.5](#).

If any individual component score is missing, the DAS28(CRP) will be missing.

### 8.1.13 Maastricht Ankylosing Spondylitis Enthesitis Index

The MASES Index comprises six two-sided and one one-sided item (bilateral costochondral 1, costochondral 7, anterior superior iliac spine, posterior iliac spine, iliac crest and proximal insertion of the achilles tendon sites, and the fifth lumbar vertebral body spinous process) ([Heuft-Dorenbosch et al, 2003](#)) each scored as 0 = not tender or 1 = tender and then summed for a possible score of 0 to 13, with higher scores indicating worse enthesitis.

If 7 or more items are available, MASES will be calculated by dividing the summed score with the number of assessments and multiplying the result by 13. If less than 7 items are available, MASES will be treated as missing.

Summaries of MASES will be restricted to subjects with a MASES >0 at PA0008 Baseline.

### 8.1.14 Leeds Dactylitis Index

Dactylitis, the swelling of an entire digit related to articular and periarticular inflammation, is a characteristic of inflammatory spondyloarthropathies, including PsA. Presence of dactylitis will be assessed using the LDI basic, which evaluates for a ≥10% difference in the circumference of the affected digit compared to the opposite digit ([Healy and Helliwell, 2007](#), [Helliwell, 2005](#)).

The percent difference in circumference (mm) between each affected digit and its opposite will be multiplied by a tenderness score for the affected digit (0 for non-tender, 1 for tender). The results from each digit with dactylitis will be summed to produce a final score at each visit.

If matching digits are both affected, the circumference of each digit will be compared to the normative value in [Table 8-5](#). If both digits have a difference in circumference from the normative value of ≥10%, then both digits will contribute to the LDI score (if they are both tender).

If the circumference of the affected digit is smaller than the unaffected digit, then the affected digit will be compared to the normative value. If a digit is affected and the circumference of the opposite digit is missing, the affected digit will be compared with the normative value.

**Table 8-5: Normative values for Leeds Dactylitis Index (mm)**

	Digit	Men	Women
Hand	Thumb	70	58
	Index	63	54
	Middle	63	54

**Table 8-5: Normative values for Leeds Dactylitis Index (mm)**

	Digit	Men	Women
	Ring	59	50
	Little	52	44
Foot	Great toe	82	72
	Second	52	46
	Middle	50	44
	Fourth	50	44
	Little	52	45

Summaries of LDI will be restricted to subjects with LDI scores >0 at PA0008 Baseline. PA0008 Baseline LDI will be taken directly from the PA0008 database without derivation. Digits that are included in the calculation of the LDI score (both tender and non-tender) will be flagged in the relevant analysis dataset.

### 8.1.15 Hospital Anxiety and Depression Scale

The HADS was chosen for its well-established psychometric properties and its use in clinical research on biological therapy in subjects with chronic plaque psoriasis (Langley et al, 2010; Dauden et al, 2009). The HADS consists of 14 items, each scored from 0 to 3.

HADS-A will be calculated as the sum of the scores for items 1, 3, 5, 7, 9, 11, 13, and HADS-D will be calculated as the sum of the scores for items 2, 4, 6, 8, 10, 12, 14. Each score ranges from 0 to 21 with higher scores indicating a worse state. A score below 8 is considered normal and a score of 15 and above is considered severe (Snaith and Zigmund, 1994). If any of the 7 items required to calculate the HADS-A or HADS-D are missing, then the HADS-A or HADS-D will be treated as missing.

A flag to identify “normal” depression and anxiety status at each visit (defined as having HADS-D <8 and HADS-A <8 at the same visit) will be derived.

### 8.1.16 Psoriatic Arthritis Impact of Disease-9

The PsAID-9 is a patient-reported outcome measure for assessing the impact of PsA in 9 physical and psychological domains, including pain, fatigue, skin problems, work and/or leisure activities, functional capacity, discomfort, sleep disturbance, coping, and anxiety/fear/uncertainty.

Each domain is assessed with a single question using a 0 to 10 numerical rating scale. Each domain score is multiplied by a weighting factor and the results are then summed to provide the total score.

$$\begin{aligned}
 PsAID - 9 = & Pain * 0.174 + Fatigue * 0.131 + Skin * 0.121 \\
 & + Work\ and/or\ Leisure\ Activities * 0.110 + Function \\
 & * 0.107 + Discomfort * 0.098 + Sleep * 0.089 + Coping \\
 & * 0.087 + Anxiety * 0.085
 \end{aligned}
 \tag{16}$$

The total score ranges from 0 to 10, with higher scores indicating a worse status. A score below or equal to 4 out of 10 is considered a patient-acceptable status. A decrease of 3 or more points from PA0008 Baseline is considered a minimal clinically important difference (MCID).

If 1 of the 9 domains is missing, the missing value is imputed using the mean of the raw values (prior to weighting) from the 8 other (non-missing) domains. If 2 or more of the domains are missing, the PsAID-9 score will be missing.

### 8.1.17 Short Form – 36 Items Health Survey

The SF-36 (Version 2, standard recall) is a 36 item generic health-related quality of life (HRQoL) instrument that uses a recall period of 4 weeks. Items are grouped into 8 component scales as follows: Physical Functioning (10 items), Role Physical (4 items), Bodily Pain (2 items), General Health (5 items), Vitality (4 items), Social Functioning (2 items), Role Emotional (3 items), Mental Health (5 items), and a further unscaled single item (Question 2) for perceived stability or change in health (Health Transition) during the last year. The concepts represented by these scales contribute to physical, mental, and social aspects of HRQoL. The classification of the questionnaire items to the health scales is shown in [Section 12.3](#).

The SF-36 PCS score and MCS score are used to measure the 2 broad components, or aspects, of health: physical and mental. PCS and MCS scores are based on the aggregate of the 8 health concepts described above and all of the 8 health scales are used to score both components.

For the calculation of the SF-36 scale scores and the component summary scores PCS and MCS, the scoring software Optum's PRO CoRE will be used (Version 1.4). The norm-based scores (based on the US 2009 general population) will be utilized for analysis. The latest updates to the software use improved methods for missing data estimation through the following:

- Dropping the previous 'half-scale' rule, so that scale scores (except the Physical Functioning scale) will be estimated when the respondent has provided a response to at least one item in the same scale.
- Using item response theory to develop a model for estimating a score on the Physical Functioning scale.
- Using regression methods to estimate the PCS and MCS on the basis of the available scales.

## 8.2 Statistical analysis of secondary efficacy variables

The following secondary efficacy variables will be summarized for the FAS, by treatment group at the completion of PA0008 and overall:

- ACR20, ACR50, and ACR70 response relative to PA0008 Baseline at PA0009 Week 48.
- Change from PA0008 Baseline value in MASES at PA0009 Week 48.
  - Only subjects with MASES >0 at PA0008 Baseline will be included.
- Change from PA0008 Baseline value in LDI at PA0009 Week 48.
  - Only subjects with LDI >0 at PA0008 Baseline will be included.
- PASI75 and PASI90 response relative to PA0008 Baseline at PA0009 Week 48.
  - Only subjects with BSA affected by psoriasis  $\geq 3\%$  at PA0008 Baseline will be included.

For ACR and PASI responses, one set of summaries will be produced using data following NRI and another set using OC data. For MASES and LDI, summaries will be produced using data following MI.

### 8.3 Statistical analysis of other efficacy variables

The following other efficacy variables will be summarized for the FAS at scheduled visits in accordance with the schedule of study assessments in [Table 2-1](#), by treatment group, at the completion of PA0008 and overall:

- ACR20, ACR50, and ACR70 response at each visit in PA0009, relative to PA0008 Baseline.
- PASI75, PASI90 and PASI100 response at each visit in PA0009, relative to PA0008 Baseline.
  - Only subjects with BSA affected by psoriasis  $\geq 3\%$  at PA0008 Baseline will be included.
- BSA at each visit in PA0009
  - The number and percentage of subjects with a BSA in the following categories at each visit will be summarized based on OC data: 0%, 1 to 3%, >3 to 10%, >10 to 20%, >20 to 30%, >30 to 40%, >40 to 50%, >50 to 60%, >60 to 70%, >70 to 80%, >80 to 90%, and >90% to 100%.
  - Only subjects with BSA affected by psoriasis  $\geq 3\%$  at PA0008 Baseline will be included.
- MDA at each visit in PA0009.
- Change from PA0008 Baseline in DAS28(CRP) at each visit in PA0009.
- Change from PA0008 Baseline in CRP (expressed as ratio to Baseline) at each visit in PA0009.
  - For CRP the rules for handling values that are lower than the LLOQ identified in PA0008 will be followed as per [Section 8.1.7](#)
- Change from PA0008 Baseline in MASES at each visit in PA0009.
  - Only subjects with MASES >0 at PA0008 Baseline will be included.
- Change from PA0008 Baseline in LDI at each visit in PA0009.
  - Only subjects with LDI >0 at PA0008 Baseline will be included.
- Change from PA0008 Baseline in PsAID-9 score at each visit in PA0009.
- Change from PA0008 Baseline in SF-36 PCS and MCS scores at each visit in PA0009.
- Change from PA0008 Baseline in HADS-A and HADS-D scores at each visit in PA0009.
- Incidence of depression and anxiety status “normal” as defined by both HADS-D<8 and HADS-A<8 at each visit in PA0009.
- Change from PA0008 Baseline in TJC at each visit in PA0009.
- Change from PA0008 Baseline in SJC at each visit in PA0009.
- Change from PA0008 Baseline in HAQ-DI score at each visit in PA0009.

- Change from PA0008 Baseline in PtAAP at each visit in PA0009.
- Change from PA0008 Baseline in PhGADA at each visit in PA0009.
- Change from PA0008 Baseline in PGADA at each visit in PA0009.

One set of summaries will be produced for all of the above parameters using data following NRI (for binary endpoints) or MI (for continuous endpoints) as appropriate, as described in Section 4.2.1. For BSA the summary will be based on OC data only.

For each of the following variables, an additional set of summaries will be produced using OC data:

- ACR
- PASI
- MDA
- MASES
- LDI

For each of the following variables, an additional set of summaries will be produced after the response variables have been derived following MI of components:

- ACR
- PASI

Finally, for PASI, supplementary summary tables will be presented for the following based on the imputation rules described in Section 4.2.2:

- PASI response derived using LOCF
- PASI response derived based on the BSA observed at the corresponding visit

The summary tables for CRP will display the absolute value and ratio to PA0008 Baseline and will contain n, geometric mean (and 95% CI), median, first and third quartiles (Q1 and Q3), minimum and maximum. Any values for the ratio to PA0008 Baseline below 0.01 will be presented as <0.01 in the listing and summary table.

### 8.3.1 Maintenance of response

ACR20, ACR50, ACR70, PASI75, PASI90 and PASI100 response relative to PA0008 Baseline will, in addition, be summarized at each post-Baseline visit in PA0008 through to PA0009 Week 104, by treatment sequence, as defined in Section 3.7. These summaries will be restricted to subjects in the FAS and who were responders for the relevant endpoint at PA0008 Week 12, and data will be reported following NRI.

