Bimekizumab has also been investigated in a Phase 1b, proof-of-concept, randomized, placebo-controlled, multiple-dose study (PA0007). A total of 53 subjects have been randomized. The primary objective of PA0007 was to assess the safety and PK of multiple dose administration of iv bimekizumab in subjects with PsA. Four active doses and a placebo were tested. Drug was administered as a loading dose of bimekizumab 80, 160, 240, or 560mg at Week 1, and 2 additional doses of bimekizumab 40, 80, 160, or 320mg at Week 4 and Week 7. In each treatment group, subjects received a total of 3 doses of bimekizumab, administered every 3 weeks. There were no unexpected clinically relevant safety findings and all doses were well tolerated. The PK was linear across the tested dose range and no change in PK was observed following multiple doses. Observed changes in inflammatory biomarkers were consistent with expectations based on the IL-17A and IL-17F mechanism of action. The exploratory analysis showed clinically relevant improvement in activity of PsA and in skin involvement in those subjects with concomitant active psoriatic lesions. Data from the top 3 bimekizumab dose groups pooled showed that, by Week 9, 80% (95% confidence interval [CI]: 62.7, 90.5) of subjects achieved an ACR20 response (vs 16.7% [95% CI: 4.7, 44.8] in the placebo group) and 100% (95% CI: 79.6, 100.0) of 26 subjects with active psoriatic lesions had achieved a PASI75 response (vs 0% [95% CI: 0.0, 43.4] in the placebo group).

Infections (mostly nasopharyngitis) were the most commonly reported events in both the active-treatment and the placebo group. None of the infections were considered serious or required treatment with antibiotics. Two subjects in the active-treatment group experienced 1 local candida infection each (oropharyngitis and vulvovaginitis) that were nonserious and resolved with topical therapy. There was a reduction in mean neutrophil count in the active-treatment group, although this drop was not clinically relevant and a clear relationship with dose or time was not evident. Some increases in liver function tests were reported, but none had a convincing relationship to exposure to study medication.

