### 2.2.2.3 Other efficacy variables

The other efficacy variables are listed below and will be evaluated at scheduled visits in accordance with the schedule of study assessments in [Table 2-1](#):

- ACR20, ACR50, and ACR70 response at each visit (PA0009 EV, Week 12, 24, 36, 48, 60, 72, 84, 96, 100, 104), relative to PA0008 Baseline.
  - ACR20, ACR50 and ACR70 response will also be reported at each post-PA0008 Baseline visit in PA0008 through to PA0009 Week 104 (PA0008 Week 2, 4, 8, 12, 16, 20, 24, 36 and PA0009 EV [PA0008 Week 48], Week 12, 24, 36, 48, 60, 72, 84, 96, 100, 104), for subjects who were responders at PA0008 Week 12. These are additional variables to those specified in the protocol and will be used to assess maintenance of response.
- PASI75, PASI90 and PASI100 response at each visit (PA0009 EV, Week 12, 24, 36, 48, 60, 72, 84, 96, 100, 104), relative to PA0008 Baseline.
  - PASI75, PASI90 and PASI100 response will also be reported at each post-PA0008 Baseline visit in PA0008 through to PA0009 Week 104 (PA0008 Week 2, 4, 8, 12, 24 and 36 and PA0009 EV [PA0008 Week 48], Week 12, 24, 36, 48, 60, 72, 84, 96, 100, 104), for subjects who were responders at PA0008 Week 12. These are additional variables to those specified in the protocol and will be used to assess maintenance of response.
  - BSA at each visit in PA0009 will also be reported. This is additional to the protocol and was added as an additional method of assessing response in order to provide information at visits where the PASI data may be missing.
- Minimal Disease Activity (MDA) at each visit (PA0009 EV, Week 12, 24, 36, 48, 72, 96, 104).
- Change from Baseline of PA0008 value in Disease Activity Score-28 based on C-reactive protein (DAS28[CRP]) at each visit (PA0009 EV, Week 12, 24, 36, 48, 60, 72, 84, 96, 100, 104).
- Change from Baseline of PA0008 in MASES at each visit (PA0009 EV, Week 12, 24, 36, 48, 72, 96, 104).
- Change from Baseline of PA0008 in the LDI at each visit (PA0009 EV, Week 12, 24, 36, 48, 60, 72, 84, 96, 100, 104).
- Change from Baseline of PA0008 in Psoriatic Arthritis Impact of Disease-9 (PsAID-9) at each visit (PA0009 EV, Week 12, 24, 36, 48, 60, 72, 84, 96, 100, 104).
- Change from Baseline of PA0008 in Short Form 36-item Health Survey (SF-36) at each visit (PA0009 EV, Week 12, 24, 36, 48, 60, 72, 84, 96, 100, 104).

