### **3.7 Treatment assignment and treatment groups**

This is an open label, single arm study.

Treatment group at the completion of PA0008 (presented as ‘BKZ 160mg’ or ‘BKZ 320mg’) and an overall ‘BKZ Total’ column will be used to summarize data in PA0009.

The endpoints assessing maintenance of ACR and PASI response over time will be summarized by treatment sequence across PA0008 and PA0009. Treatment sequences take the form ‘A/B/C’, where A is the treatment in the first 12 weeks of PA0008, B is the treatment from Week 12 to Week 48 of PA0008, and C is the treatment in PA0009. The seven planned treatment sequences are as follows:

- Placebo/BKZ 160mg/BKZ 160mg.
- Placebo/BKZ 320mg/BKZ 160mg.
- BKZ 16mg/BKZ 160mg/BKZ 160mg.
- BKZ 16mg/BKZ 320mg/BKZ 160mg.
- BKZ 160mg loading dose (LD)/BKZ 160mg/BKZ 160mg.
- BKZ 160mg/BKZ 160mg/BKZ 160mg.
- BKZ 320mg/BKZ 320mg/BKZ 160mg.

For safety summaries the following will be presented:

- Safety summaries including PA0009 data only will be presented by treatment group at the completion of PA0008 and overall.
- Safety summaries including data from both PA0008 and PA0009 combined will be presented for 'BKZ 160mg', 'BKZ 320mg', and 'BKZ Total'. The assignment of each of the sequences to the columns in this table is presented in [Table 3-2](#).
  - The 'BKZ 160mg' treatment column in these tables will include subjects in both the BKZ 160mgLD and BKZ 160mg treatment groups.
  - For each column, only those periods for which the specified treatment is received will contribute to the summary ie, for sequence BKZ 16mg/BKZ 320mg/BKZ 160mg, the 16mg period will contribute to the BKZ Total column only, the BKZ 320mg period will contribute to the BKZ 320mg column and the BKZ Total column only, and the BKZ 160mg period will contribute to the BKZ 160mg column and the BKZ Total column only.

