## 8 EFFICACY ANALYSES

Missing efficacy data will be imputed as described in [Section 4.2.1](#) prior to reporting. As a sensitivity analysis, summaries will be repeated based on non-imputed (OC) data for the following variables:

- ACR20, ACR50 and ACR70 response relative to PA0008 Baseline at each visit in PA0009.
- PASI75, PASI90 and PASI100 response relative to PA0008 Baseline at each visit in PA0009.
- MDA at each visit in PA0009.
- Change from PA0008 Baseline in MASES at each visit in PA0009.
- Change from PA0008 Baseline in LDI at each visit in PA0009.

A further sensitivity analysis will be performed for ACR20, ACR50 and ACR70, PASI75, PASI90 and PASI100 responses relative to PA0008 Baseline at each visit. The response endpoint will be re-derived and summarized based on the mean value (across multiple imputations) of the ACR component scores or PASI total score after imputation for missing data.

Efficacy variables will be summarized and listed (including individual raw data and derived domain and total scores, where applicable) for the FAS. Summaries of MASES will be restricted to subjects with a MASES  $>0$  at PA0008 Baseline, of LDI will be restricted to subjects with a LDI  $>0$  at PA0008 Baseline, and of PASI responses will be restricted to subjects with a BSA affected by psoriasis of  $\geq 3\%$  at PA0008 Baseline. Maintenance of response summaries will be restricted to subjects with a response at PA0008 Week 12 for the specific endpoint (where response at PA0008 Week 12 is taken directly from the PA0008 datasets).

Responder variables (eg, ACR20 response) will be derived relative to the PA0008 Baseline and summarized using n and percentage at each visit, by treatment group at completion of PA0008 and overall.

Maintenance of response will be assessed for ACR20, ACR50, ACR70, PASI75, PASI90 and PASI100. The responses will be derived relative to PA0008 Baseline and summarized using n and percentage at each post-PA0008 Baseline visit, by treatment sequence across PA0008 and PA0009. These summaries will therefore include PA0008 Week 2, 4, 8, 12, 16 (for ACR only), 20 (for ACR only), 24, and 36 and PA0009 EV [PA0008 Week 48], Week 12, 24, 36, 48, 60, 72, 84, 96, 100, and 104, for subjects who were responders at PA0008 Week 12.

Absolute and change from PA0008 Baseline for all continuous efficacy variables will be summarized descriptively by visit, by treatment group at completion of PA0008, and overall.

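### In the two placebo-start sequences, the maintenance-of-response summaries follow Week 12 placebo responders and omit subjects who first responded on bimekizumab after Week 12

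*SAP*

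**What the plan says.** SAP 8.3.1 plans ACR20/50/70 and PASI75/90/100 response at every post-Baseline visit from PA0008 through PA0009 Week 104, by treatment sequence, after nonresponder imputation. On who is included, it says: "These summaries will be restricted to subjects in the FAS and who were responders for the relevant endpoint at PA0008 Week 12". SAP 8 repeats the rule ("Maintenance of response summaries will be restricted to subjects with a response at PA0008 Week 12 for the specific endpoint") and gives the source of the qualifying status ("where response at PA0008 Week 12 is taken directly from the PA0008 datasets"). SAP 2.2.2.3 uses the same restriction ("for subjects who were responders at PA0008 Week 12. These are additional variables to those specified in the protocol") and, like SAP 3.10, says the purpose is to assess maintenance of response. None of these sections gives any sequence a different anchor.

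SAP 3.7 writes each sequence as A/B/C, "where A is the treatment in the first 12 weeks of PA0008, B is the treatment from Week 12 to Week 48 of PA0008", with C the treatment in PA0009. Two of the seven sequences begin with placebo. One is "Placebo/BKZ 160mg/BKZ 160mg"; the other has 320mg as its middle element.

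**The concern.** A maintenance table should start from a response to the treatment whose durability is in question. In the two placebo-start sequences the qualifying response comes after 12 weeks of placebo. Later visits in those columns show what happened to placebo responders once they began bimekizumab. A placebo-start subject who was a nonresponder at Week 12 and then responded on bimekizumab fails the filter and never appears.

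The display was added to the plan for a stated purpose, and in two of seven sequences it does not serve that purpose. The combined PA0008/PA0009 safety analyses do separate the two treatments: SAP 10.1 starts bimekizumab duration at the first bimekizumab dose, and SAP 10.2 drops adverse events with onset on placebo from those displays.

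**Working it through.** The plan gives no sample size, power or expected count for this display, so there is no figure to reproduce. The check is a cross-reading, followed by an illustration of scale.

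**1. When the placebo sequences switch.** SAP 3.7 puts the change from A to B at Week 12. SAP 3.10 agrees: it says subjects had at least 36 weeks on a constant 160mg or 320mg dose before PA0009 entry at PA0008 Week 48, and 48 − 12 = 36. The SAP does not say in words that the Week 12 assessment came before the first bimekizumab dose. Even if both fell on the same day, the response would reflect 12 weeks of placebo.

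**2. Who passes the filter.**

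| Placebo-start subject | Week 12 status | In maintenance table? |
|---|---|---|
| Responds on placebo | Responder | Yes |
| First responds on bimekizumab | Nonresponder | No |
| Responds at both Week 12 and Week 24 | Responder | Yes |

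**3. Whether another table fills the gap.** The by-visit ACR and PASI summaries (SAP 8, 8.3) use the FAS, with PASI limited to BSA of at least 3% at PA0008 Baseline. They are split by treatment group at completion of PA0008, so placebo-start and active-start subjects are pooled, and they do not condition on an earlier response. SAP 3.10 drops summaries by randomized treatment. No maintenance summary has a later anchor.

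**4. Scale for ACR20 (illustration only).** Inputs:
- Number of placebo-start subjects, N: not in the documents. PA0008 has 200 subjects; 200/5 = 40 if five groups were equal. Assumed 40, range 30 to 50.
- PA0007 Week 9 ACR20 (Protocol 2.1.1): placebo 16.7% (95% CI 4.7 to 44.8); top three doses pooled 80% (62.7 to 90.5). Wilson intervals for 2/12 and 24/30 reproduce these limits.
- All subjects are assumed to roll over and enter the FAS.

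Expected number anchored at Week 12 = N × placebo rate:
- 40 × 0.167 = 6.7, or about 3.3 per sequence if split equally.
- With N = 40 over the CI: 40 × 0.047 = 1.9 to 40 × 0.448 = 17.9.
- Over the CI and the range of N: 30 × 0.047 = 1.4 to 50 × 0.448 = 22.4.

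Expected number anchored at Week 24, after 12 weeks of bimekizumab = N × active rate:
- 40 × 0.80 = 32.
- With N = 40 over the CI: 40 × 0.627 = 25 to 40 × 0.905 = 36.
- Over the CI and the range of N: 30 × 0.627 = 19 to 50 × 0.905 = 45.

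**5. Scale for PASI75.** PA0007 placebo was 0% (CI 0 to 43.4). The upper limit is that of a Wilson interval for 0/5, so the estimate is very imprecise. Even if all subjects had BSA of at least 3%, the range would be 0 to 50 × 0.434 = 21.7. The number who meet that BSA condition is not given.

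**6. Follow-up after the anchor, to PA0009 Week 104.** Week 12 anchor: (48 − 12) + 104 = 140 weeks. Week 24 anchor: (48 − 24) + 104 = 128 weeks.

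**The case against.** The best defence is that nothing is hidden or contradictory. The SAP states the population, sequences and imputation rule exactly, and it speaks of maintenance of response without saying that the response must be to bimekizumab. The columns carry the sequence name, so a reader can see that the first 12 weeks were placebo. No pooled maintenance column is specified, so placebo responders do not enter the five sequences that start on bimekizumab. Maintenance is an added 'other' variable in a descriptive study whose primary objective is safety.

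All of this stands, and it limits the weight of the point. It does not supply the missing summary. A correctly labelled column of placebo responders still says nothing about how long a bimekizumab response lasts in placebo-start subjects.

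A second objection also stands: moving only the placebo columns to Week 24 within the existing table would mix anchor visits and follow-up lengths across columns. It would also leave the two 16mg sequences anchored on a dose that is replaced at Week 12. The fix below therefore uses a separate table.

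A reader might infer three stronger things that the documents do not support:
- That the maintenance analysis is unsound as a whole. It is not; five of the seven columns do not depend on a placebo response.
- That later responders are lost to the efficacy analysis. They remain in the by-visit FAS summaries and listings.
- That the placebo PASI columns will be empty. An interval of 0 to 43.4% allows that but does not establish it.

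**Conclusion.** The point holds, within limits. In two of seven sequences the maintenance display follows placebo responders and omits subjects who first responded on bimekizumab after Week 12, and no other planned table conditions on a bimekizumab response in those subjects. This follows from SAP 3.7 and 8.3.1 read together and needs no numerical assumption. No primary or secondary result changes.

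The size is only indicative: about 7 subjects anchored for ACR20 at Week 12 (1.4 to 22.4 over arm size and CI), against about 32 of 40 at Week 24 (25 to 36 over the CI at that arm size). These counts rest on an assumed arm size, full rollover, and Week 9 rates from a different study with intravenous dosing. The difference between them should not be read as a reliable gain.

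Because the correction is cheap and uses data already collected, it is worth making.

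**What to change.** In SAP 2.2.2.3, 3.10, 8 and 8.3.1:

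1. Keep the Week 12 table, but label the two placebo columns 'placebo responders at Week 12' and state that they are not to be read as maintenance of a bimekizumab response.
2. Add a separate maintenance summary for the two placebo-start sequences, restricted to responders at PA0008 Week 24, after 12 weeks of bimekizumab. SAP 2.2.2.3 lists Week 24 for both ACR and PASI. Show post-anchor visits by weeks since anchor.
3. Footnote the Week 12 table to say that the two BKZ 16mg sequences are anchored on response to 16mg, before the dose change at Week 12.

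The cost is SAP wording, one additional selection flag and one extra set of tables; no new data are needed. The added summary has 128 weeks of post-anchor follow-up rather than 140. Keeping the Week 12 table also preserves comparability with any displays already produced from the Week 60 snapshot (SAP 4.3).
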